### 1. Abstract

This is a prospective double-blind, randomized, placebo-controlled trial aims to investigate whether add-on of a standardized extract of cultured Lentinula edodes mycelia (AHCC®) can enhance the effect of immunotherapy in cancer patients.

AHCC is a newly developed functional food. In vitro studies have demonstrated that AHCC enhances natural killer cell activity and may serve as a potent biological response modifier for cancer treatment. Previous research involving 269 HCC patients found that 113 patients who took AHCC orally after curative surgery (AHCC group) experienced significantly longer recurrence-free survival (hazard ratio [HR], 0.639; 95% confidence interval [CI], 0.429-0.952; P = 0.0277) and overall survival (HR, 0.421; 95% CI, 0.253-0.701; P = 0.0009) compared to the control group.

This trial will adopt a two-arm Bayesian optimal phase 2 (BOP2) design (Zhao, 2020). The study will simultaneously evaluate efficacy and toxicity. The null hypothesis assumes a true response rate of 0.27 and a grade 3/4 toxicity rate of 0.57, while the alternative hypothesis assumes a true response rate of 0.42 and a grade 3/4 toxicity rate of 0.36. The trial will be conducted in two stages. In the first stage, 36 patients will be recruited and randomized using block randomization with a block size of 4. The study will be terminated early if fewer patients respond in the AHCC group than in the control group or if 2 or more patients in the AHCC group experience grade 3/4 acute toxicity compared to the control group. Otherwise, the second stage will proceed with the recruitment of an additional 58 patients, bringing the total sample size to 94. If, among the 47 patients in the AHCC group, at least 2 more patients respond compared to the control group or if 2 or fewer patients experience grade 3/4 toxicity, we will reject the null hypothesis and conclude that the treatment is promising. This design controls the type I error rate at 0.1 and achieves a power of 0.75. Considering a 5% dropout rate, each group will enroll 49 patients, resulting in a total sample size of 98.

Following the Screening period to confirm eligibility, 98 study participants, who meet the entry criteria, will be 1:1 randomized to study intervention (3g of AHCC oral per day or matching placebo) and will be stratified by AFP (<400 vs. ≥400). Enrollment is anticipated to be completed within 2 years, with each participant followed for 6 months since treatment. Therefore, the total duration of the study is expected to be approximately 2.5 years from the time of Institutional Review Board approval. All enrolled participants will receive AHCC or placebo 3g per day until disease progression, intolerance or patient or physician decision to discontinue. Tumor tissue and peripheral blood samples will be collected from all participants for biomarker analysis.

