### 11. Statistical consideration

- 11.1 The primary endpoint is ORR in AHCC arm compared to placebo arm. The secondary endpoints include, incidence and severity of adverse events according to CTCAE version 4, progression-free survival and overall survival.
- 11.2 Exploratory endpoints will include correlation of treatment response (tumor shrinkage, objective response rate, etc.) with immune biomarkers in subjects' samples from tumor tissue and peripheral blood.
- 11.3 We simultaneously monitor efficacy and safety endpoints using the 2-arm Bayesian optimal phase 2 (BOP2) design (Zhao et al., 2020).
- 11.3.1 Specifically, let n denote the interim sample size and N denote the maximum sample size. Let E and C denote the experimental arm and the control arm, respectively. For arm t, t = E, C, let  $Y_{eff,t}$  and  $Y_{tox,t}$  respectively denote the efficacy and toxic endpoints, with  $Y_{eff,t} = 1$  and  $Y_{tox,t} = 1$  respectively indicating that patients experience efficacy and toxicity. We assume that the joint distribution of  $\left(Y_{eff,t}, Y_{tox,t}\right)$  follows a multinomial distribution with four elementary

the joint distribution of  $(1_{eff,t},1_{tox,t})$  follows a martinormal distribution with four elementary

outcomes:  $\left(Y_{eff,t},Y_{tox,t}\right)$  = (1, 1), (1, 0), (0, 1) and (0, 0). Let  $\mathbf{p_t} = \left(P_{11,t},P_{10,t},P_{01,t},P_{00,t}\right)$ 

denote the probabilities of observing the four outcomes, and let  $p_{eff,t} = Pr(Y_{eff,t} = 1)$ ,

$$p_{tox,t} = Pr(Y_{tox,t} = 1)$$
 and  $p_{efftox,t} = Pr(Y_{eff,t} = 1, Y_{tox,t} = 1)$ .

11.3.2 The experimental arm is deemed as unacceptable if  $H_0$ :  $p_{eff,E} \leq p_{eff,C}$  or  $p_{tox,E} > p_{tox,C}$ , i.e., the experimental treatment is inefficacious or overly toxic, with respect to the control. We employ the following Bayesian rule to make a go/no-go decision: (Futility and toxicity stopping) stop enrolling patients and claim that the experimental arm is unacceptable if

$$Pr(p_{eff,E} > p_{eff,C}|data) < \lambda \left(\frac{n}{N}\right)^{\alpha}$$
,

[figure not shown]
OR

$$Pr(p_{tox,E} \leq p_{tox,C}|data) < \lambda \left(\frac{n}{N}\right)^{\alpha}$$
,

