where  $\lambda$ =0.68 and  $\alpha$ =0.84 are design parameters optimized to maximize the probability of correctly concluding an efficacious and safe treatment as acceptable when  $p_{eff,E}=0.42$ ,  $p_{tox,E}=0.36$  and  $p_{efftox,E}=0.15$ , while controlling that the probability of incorrectly claiming an inefficacious and toxic treatment, with  $p_{eff,C}=p_{eff,E}=0.27$ ,  $p_{2,C}=p_{2,E}=0.57$  and  $p_{3,C}=p_{3,E}=0.15$ , as acceptable is 10 %. This optimization is performed assuming a vague Dirichlet prior Dir(0.25,0.25,0.25,0.25) for  ${\bf p}$ . The prior is chosen such that it corresponds to a prior effective sample size of 1. The above decision rule leads to the optimal stopping boundaries shown in following tables. The trial stops when either the efficacy endpoint or the toxicity endpoint crosses the stopping boundaries.

[figure not shown]
Optimized stopping boundaries for efficacy endpoint

Interim (no. in control)	Interim (no. in experimental)	No. response (eff) in control	Stop for futility if no. of response in experimental - no. of response in control <=
18	18	0	Never
18	18	1~2	-1
18	18	3~16	-2
18	18	17~18	-1
47	47	0~2	0
47	47	3~12	1
47	47	13~32	2
47	47	33~44	1
47	47	45~47	0

Optimized stopping boundaries for toxicity endpoint

			Stop for unsafety if no. of toxicity in
Interim (no.	Interim (no. in	No. toxicity (tox)	experimental - no. of toxicity in
in control)	experimental)	in control	control >=
18	18	0~1	1
18	18	2~15	2
18	18	16~17	1
18	18	18	Never
47	47	0~3	0
47	47	4~14	-1
47	47	15~34	-2
47	47	35~45	-1
47	47	46~47	0

Based on the above tables and figures, we perform the interim analysis when the number of enrolled patients reaches 36. When the total number of patients reaches the maximum sample size of 94, we reject the null hypothesis and conclude that the experimental arm is acceptable, compared to the control, if both the futility and toxicity stopping boundary are not crossed. Below are the operating characteristics of the design based on 10000 simulations using the BOP2 web application, which is available at http://www.trialdesign.org. Operating characteristics

			Pr(Eff						
			&				Early		
	Pr(Eff	Pr(To	Tox)		Pr(Tox)	Pr(Eff &	Futilit		Avera
	) for	x) for	for	Pr(Eff) for	for	Tox) for	У	Claim	ge
Scena	Contr	Contr	Contr	Experime	Experime	Experime	Stoppi	Promisi	Sampl
rio	ol	ol	ol	ntal	ntal	ntal	ng (%)	ng (%)	e Size
1	0.27	0.57	0.15	0.37	0.47	0.17	23.58	44.40	80.3

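### The Abstract calls AHCC promising if the response or the toxicity criterion is met, whereas Section 11.3 requires both; the stated 10% type I error belongs only to the Section 11.3 rule

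*Protocol*

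**What the plan says.** **Final decision, Abstract (Section 1).** Among 47 patients per arm, the null hypothesis is rejected if "at least 2 more patients respond compared to the control group or if 2 or fewer patients experience grade 3/4 toxicity, we will reject" it. The Abstract then states: "This design controls the type I error rate at 0.1 and achieves a power of 0.75".

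**Final decision, Section 11.3.** At 94 patients the protocol will "conclude that the experimental arm is acceptable, compared to the control, if both the futility and toxicity stopping boundary are not crossed". Section 11.3.2 defines an unacceptable arm as one where "the experimental treatment is inefficacious or overly toxic, with respect to the control".

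**Interim decision, Abstract.** "The study will be terminated early if fewer patients respond in the AHCC group than in the control group". It also stops if 2 or more AHCC patients have grade 3/4 acute toxicity, worded as a comparison with control.

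**Interim decision, Section 11.3.** "The trial stops when either the efficacy endpoint or the toxicity endpoint crosses the stopping boundaries". The tabled cut-offs depend on the control count. At 18 per arm with 3 to 16 control responders, the trial stops for futility at a deficit of 2 or more responders.

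**The concern.** The null hypothesis is a union: not better on response, or worse on toxicity. Rejecting a union requires evidence against both parts, which is what Section 11.3 asks for. The Abstract accepts evidence against either part, so it is a more permissive test, yet it carries the error rates of the stricter one.

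The Abstract's final toxicity clause also has no comparator. It can mean at most 2 toxic patients in the AHCC arm, at least 2 fewer than control, or at most 2 more than control.

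At stake is the trial's go/no-go criterion. A reader working from the Abstract could call AHCC promising on one criterion alone. On all three readings that includes trials in which toxicity is no lower than in control; on the two comparative readings it also includes trials with no gain in response.

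**Working it through.** **Inputs (all from the protocol).** Null: "The null hypothesis assumes a true response rate of 0.27 and a grade 3/4 toxicity rate of 0.57", with joint probability 0.15, in both arms (Abstract; Section 11.3.2). Alternative for AHCC: response 0.42, toxicity 0.36, joint 0.15. Scenario 1 for AHCC: 0.37, 0.47, 0.17. Allocation 1:1; interim at 36 patients (18 per arm), maximum 94 (47 per arm, so 29 more per arm).

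**Method.** Each arm's outcomes are drawn from a multinomial distribution with cell probabilities (joint, response − joint, toxicity − joint, 1 − response − toxicity + joint). At the null these are 0.15, 0.12, 0.42 and 0.31. Each simulated trial draws 18 and then 29 patients per arm and applies the rule under test. There were 5,000,000 simulated trials per scenario.

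**Step 1: reproduce the protocol's own figures.** Section 11.3 tables at scenario 1:

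| | Simulated | Printed |
|---|---|---|
| Early stopping | 23.6% | 23.58% |
| Promising | 43.7% | 44.40% |
| Average sample size | 80.3 | 80.3 |

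The printed values rest on 10,000 simulations, so the standard error of 44.40% is √(0.444 × 0.556 / 10,000) = 0.5 points. The gap of 0.7 points is about 1.4 standard errors.

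The same tables give a type I error of 8.9%, which respects 0.1 as a ceiling, and power of 75.3%, which matches 0.75.

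**Step 2: apply the Abstract's rule.** Interim: stop if the response difference (AHCC − control) is below 0 or the toxicity difference is at least 2. Final: go if the response difference is at least 2 or the toxicity clause is met.

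| Reading of the final toxicity clause | Null | Alternative | Scenario 1 |
|---|---|---|---|
| At most 2 AHCC patients | 21.2% | 78.2% | 58.5% |
| At least 2 fewer than control | 30.5% | 83.8% | 67.0% |
| At most 2 more than control | 36.7% | 84.0% | 68.7% |
| *Section 11.3 rule, for comparison* | 8.9% | 75.3% | 43.7% |

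Combining the Section 11.3 interim tables with the Abstract's final rule gives 23% to 45% at the null over the three readings.

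**Step 3: find the cause.** Keeping the Section 11.3 tables and only replacing the requirement for both criteria by either one raises the type I error from 8.9% to 32.9%. The conjunction drives the inflation.

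**Step 4: test whether changing the conjunction alone repairs the Abstract.** With the Abstract's cut-offs and both criteria required:

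- At least 2 fewer than control: type I error 10.6%, power 76.0%.
- At most 2 more than control: type I error 17.6%, power 78.0%.
- At most 2 AHCC patients: power about 0, because P(at most 2 of 47) at a rate of 0.36 is 3 × 10⁻⁷.

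**Step 5: what the Abstract's rule lets through at the null.** In the order of the table in step 2, it says go with no response gain in 0%, 7.2% and 12.1% of trials, and with toxicity no lower than control in 8.6%, 8.6% and 13.1%.

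**Step 6: other mismatches.**

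- Interim futility: a deficit of 1 responder in the Abstract, 2 in the table (control 3 to 16). Early stopping at the alternative is 16.0% under the Abstract and 10.3% under the tables.
- Final response margin: 2 in the Abstract. The table requires 2 when control has 3 to 12 responders (probability 0.49 at a rate of 0.27) and 3 when control has 13 to 32 (probability 0.51).
- Final toxicity: the table stops at a difference of −2 or higher when control has 15 to 34 toxic patients, so at least 3 fewer than control are needed. No reading of the Abstract gives that margin.
- The texts agree on the interim toxicity cut-off when control has 2 to 15 toxic patients.

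**The case against.** The strongest reply is that the design itself is sound. Section 11.3 gives the hypotheses, the Bayesian rule, its parameters, the prior, both tables and an explicit requirement for both criteria, and it holds its error rate. The Abstract names the same BOP2 design and can be read as a loosely worded summary. The reading that best fits its hypotheses (at least 2 fewer than control), with both criteria required, gives 10.6% and 76.0%, close to the stated figures. That suggests a drafting slip and not a rival design. The count reading is also implausible, since the alternative itself implies about 47 × 0.36 = 17 toxic AHCC patients. All of this stands, and it limits the point to a contradiction between two texts. It does not remove the contradiction: the protocol names no governing text, and the Abstract ties the error rates to the wrong rule.

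A second reply is that the range rests on reading the Abstract's interim toxicity clause as a difference from control. Read as a plain count of 2 or more AHCC patients, over 99.99% of null trials would stop at stage 1 and the type I error would be about 0. That is correct, so the range must be given with this condition. But the interim clause does name control as its comparator, and the count reading would leave power near 0, so it cannot be the rule behind a power of 0.75.

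**Conclusion.** The concern holds. The protocol contains two incompatible final decision rules, and the stated 0.1 and 0.75 are delivered by the Section 11.3 rule (8.9% and 75.3%), not by the rule beside which the Abstract prints them. The Abstract's rule has a type I error of 21% to 37%: more than twice the stated 10% on each of the three readings of its final toxicity clause, and 30.5% on the reading that best fits the hypotheses. These figures assume the protocol's null rates and joint probability of 0.15, the Abstract's own interim rule, and its interim toxicity clause read as a difference from control. An analyst who follows Section 11.3 applies a coherent rule with the intended error rates. The defect is that the protocol does not tell that analyst to do so. Because it concerns the trial's success criterion, it must be fixed.

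**What to change.** Replace the Abstract's stage 1 and stage 2 sentences with the Section 11.3 rule: stop at 18 per arm, or fail at 47 per arm, if either tabled boundary is crossed; conclude promising only if neither is crossed. State that the Section 11.3 tables govern.

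If the Abstract is to summarise the final cut-offs, give both with their comparator and join them by *and*: at least 2 more responders than control when control has 3 to 12 (at least 3 more when control has 13 to 32), and at least 3 fewer patients with grade 3/4 toxicity than control when control has 15 to 34. Changing only the conjunction would leave the toxicity clause undefined and the margins at odds with the tables.

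The cost is Abstract wording only. Sample size, boundaries and trial conduct do not change.

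### The Abstract's go/no-go rule differs from section 11.3, and the type I error of 0.1 printed beside it belongs to the section 11.3 boundaries, at their calibration null

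*Protocol*

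**What the plan says.** Two places in the protocol describe the decision rule.

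- **Section 1, Abstract.** The null is a single point: "The null hypothesis assumes a true response rate of 0.27 and a grade 3/4 toxicity rate of 0.57". The alternative is response 0.42 and toxicity 0.36. At 36 patients, "The study will be terminated early if fewer patients respond in the AHCC group than in the control group"; the trial also stops if 2 or more AHCC patients have grade 3/4 acute toxicity compared with control. At 94 patients, AHCC is promising if "at least 2 more patients respond compared to the control group or if 2 or fewer patients experience grade 3/4 toxicity". The error statement follows directly: "This design controls the type I error rate at 0.1 and achieves a power of 0.75".
- **Section 11.3.** The arm is unacceptable, and this is labelled H0, if "the experimental treatment is inefficacious or overly toxic, with respect to the control". The two design parameters were chosen "while controlling that the probability of incorrectly claiming an inefficacious and toxic treatment", with both arms at response 0.27, toxicity 0.57 and joint probability 0.15, at 10%. Boundary tables are given for 18+18 and 47+47. The final decision is worded "we reject the null hypothesis and conclude that the experimental arm is acceptable, compared to the control". It carries a condition that covers both endpoints: "if both the futility and toxicity stopping boundary are not crossed".

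Section 11.1 names ORR as the only primary endpoint.

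**The concern.** The two places give different go/no-go rules under one error rate. A trial that meets only the response condition, or only the toxicity condition, is promising under the Abstract and not under section 11.3. A one-responder deficit at the interim stops the trial under the Abstract and usually does not under section 11.3. If 0.1 belongs to only one of these rules, a reader who applies the other will overstate the strength of a positive result.

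There is also a narrower mismatch inside section 11.3. The 10% was set where AHCC is no better on either endpoint, but the hypothesis labelled H0, and later said to be rejected, is true as soon as AHCC fails on one of them. With ORR as the primary endpoint, the case to watch is a product that reduces toxicity and does nothing for response.

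**Working it through.** **Rules side by side.** Expected control counts at the null show which boundary band matters: 18 × 0.27 = 4.9 responses and 18 × 0.57 = 10.3 toxicities at the interim; 47 × 0.27 = 12.7 and 47 × 0.57 = 26.8 at the end.

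| Decision | Abstract | Section 11.3 tables |
|---|---|---|
| Interim futility stop (AHCC minus control responders) | −1 or lower | −2 or lower for 3–16 control responses; −1 or lower for 1–2 or 17–18; never for 0 |
| Interim toxicity stop | excess of 2 or more (as read here) | excess of 2 or more for 2–15 control toxicities; 1 or more for 0–1 or 16–17; never for 18 |
| Final response condition | difference of at least 2 | at least 2 for 3–12 control responses; at least 3 for 13–32 |
| Final toxicity condition | 2 or fewer (ambiguous) | at least 3 fewer than control for 15–34 control toxicities; at least 2 fewer for 4–14 or 35–45 |
| How the final conditions combine | or | both |

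**Method.** Each arm is a four-cell multinomial with cells joint, response minus joint, toxicity minus joint, and the remainder. There are 18 patients per arm, then 29 more (47 − 18). Each scenario has at least 1,000,000 simulated trials. Triples below are response/toxicity/joint, and control is 0.27/0.57/0.15 unless stated.

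**Step 1: reproduce the plan's own figures with the section 11.3 tables.**

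| AHCC | Quantity | Simulated | Printed |
|---|---|---|---|
| 0.27/0.57/0.15 | promising | 0.089 | 0.1 |
| 0.42/0.36/0.15 | promising | 0.752 | 0.75 |
| 0.37/0.47/0.17 | promising | 43.6–43.7% | 44.40% |
| 0.37/0.47/0.17 | early stop | 23.6% | 23.58% |
| 0.37/0.47/0.17 | mean sample size, 36 + 58 × (1 − 0.236) | 80.3 | 80.3 |

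So 0.1 and 0.75 are the properties of the section 11.3 boundaries at those two points.

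**Step 2: apply the Abstract's rule**, with its interim toxicity clause read as an excess of 2 or more over control.

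| Reading of the final toxicity clause | Promising at null | Promising at alternative |
|---|---|---|
| AHCC count of 2 or fewer (literal) | 0.21 | 0.78 |
| at least 2 fewer than control | 0.31 | 0.84 |
| at most 2 more than control | 0.37 | 0.84 |
| at least 2 fewer, with the conditions joined by *and* instead of *or* | 0.11 | 0.76 |

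Each of the three *or* readings is at least double 0.1. The last row is not what the Abstract prints. It shows that the connective accounts for most of the gap. If the interim toxicity clause is also read as an AHCC count of 2 or more, nearly every trial stops (promising in under 0.001 at the null and 0.003 at the alternative), which does not match the printed figures either.

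**Step 3: section 11.3 tables at other points where the H0 of 11.3.2 is true.**

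| AHCC | Why H0 is true | Promising |
|---|---|---|
| 0.27/0.52/0.15 | response unchanged | 0.14 |
| 0.27/0.47/0.15 | response unchanged | 0.20 |
| 0.27/0.36/0.15 | response unchanged | 0.28 |
| 0.42/0.58/0.15 | toxicity higher | 0.22 |
| 0.42/0.62/0.15 | toxicity higher | 0.13 |
| 0.22/0.36/0.15 | response lower | 0.14 |
| 0.22/0.62/0.15 | both worse | 0.02 |
| both arms 0.20/0.50/0.10 | equal arms | 0.09 |
| both arms 0.35/0.45/0.15 | equal arms | 0.08 |

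The 0.28 moves only between 0.27 and 0.30 over the possible AHCC joint probabilities (0.27 down to 0). The 0.22 moves between 0.17 and 0.24 (joint 0.42 down to 0).

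**The case against.** The case against has four parts.

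- **The Abstract states its own point null, and section 11.3 prints the calibration in full.** This stands. No number is miscalculated, and the protocol never claims in terms that 0.1 holds over the whole either/or hypothesis. That limb is a mismatch of labels and is secondary.
- **The Abstract's rule is a faulty summary; section 11.3 operates.** This is probably how it arose, since joining the conditions with *and* brings the result close to the printed figures. But the protocol does not say which passage governs, and the error rate is printed beside the rule that lacks it.
- **The 0.21 to 0.37 range rests on guessed readings of an unclear sentence.** True, which is why all of them are shown. None of the *or* readings tried gives 0.1 and 0.75.
- **Other operating-characteristics rows may have been lost from the available text.** That cannot be ruled out, so the absence of such rows is not held against the plan.

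Stronger readings are tempting and are not supported. A reader might infer that 0.1 holds at one point only; it also holds, as an upper limit, at the other equal-arm nulls in the last table. A reader might infer that the rate is below 0.1 everywhere in H0 apart from the headline cases; 0.42/0.62/0.15 and 0.22/0.36/0.15 show otherwise. Nor does any of this show that the section 11.3 boundaries are faulty: they deliver what they were calibrated to deliver.

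**Conclusion.** Wrong as written. The Abstract and section 11.3 contradict each other on the interim and final rules, and the printed error rate is true only of the section 11.3 boundaries: about 0.09 at the stated null, against about 0.21 to 0.37 for the Abstract's rule. The range assumes a joint probability of 0.15 in both arms and an interim toxicity clause that means an excess over control.

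Secondarily, 0.1 is not controlled over the H0 labelled in 11.3.2. It is exceeded when one endpoint is null or somewhat worse and the other improves enough, reaching about 0.28 with response unchanged and toxicity at the plan's own alternative value of 0.36. It stays below 0.1 at some other points of H0. A promising result is therefore a joint go decision and should not be read as a test of ORR at the 10% level.

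**What to change.** 1. Reconcile the Abstract's interim and final rules with the section 11.3 tables, so that a promising claim requires that neither boundary is crossed.
2. State in the Abstract and in 11.3: *Under the section 11.3 boundaries, the probability of claiming AHCC promising is controlled at 0.1 at the calibration null (both arms ORR 0.27, grade 3/4 toxicity 0.57, joint 0.15) and is about 0.75 at 0.42/0.36/0.15. It is not controlled at 0.1 over the whole of the either/or hypothesis in 11.3.2, so a promising result is a joint go decision and not a 10%-level test of ORR.*
3. Report operating characteristics, with control 0.27/0.57/0.15 and AHCC joint 0.15, for ORR 0.27 with toxicity 0.36 (about 0.28) and ORR 0.42 with toxicity 0.58 (about 0.22).

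The cost is wording and two simulated scenarios. The section 11.3 boundaries and the sample size stay as they are. The price is an error statement that is narrower and less favourable than the present one.

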- 11.4 The primary endpoint analysis and other secondary endpoints will be based on the intent-to-treat population and per-protocol population, while the safety data will be summarized based on the intent-to-treat population.
  - 11.4.1 Intent-to-treat population refers to all enrolled patients regardless of their compliance with the study drug treatment.
- 11.4.2 Per-protocol population refers to all patients who have received at least 6 weeks (2 cycles) of study medication and received the first scheduled assessment of tumor response.
  - 11.5 Disease stabilization rate (complete response + partial response by RECIST + stable disease by RECIST that last for  $\geq 8$  weeks), objective response rate (complete response + partial

- response by RECIST), and down-staging rate will be calculated with their 95% confidence intervals.
- 11.6 Progression-free survival, time-to-tumor progression, and overall survival will be calculated by the Kaplan-Meier method.
- 11.6.1 Progression-free survival is defined as the duration from the date of the first dose of study drug treatment to the date of documented disease progression or death of any cause.
- 11.6.2 Time-to-tumor progression is defined as the duration from the date of the first dose of study drug treatment to the date of documented tumor progression by imaging studies.
- 11.6.3 Overall survival is defined as the duration from the date of the first dose of study drug treatment to the date of death of any cause.
  - 11.7 The baseline and changes in immune-related biomarkers after study drug treatment will be correlated with the patients' treatment outcome, including disease stabilization, best radiographic response, time to tumor progression, progression-free survival, and overall survival.
  - 11.8 For the endpoint of the safety assessment, the tabulations will count the number of subjects reporting individual adverse events. Incidence of adverse events and serious adverse events will be summarized.
  - 11.9 The demographic features of the subjects will be summarized by descriptive statistics. Comparison between sub-groups, for examples, subjects with vs. without objective tumor response/AFP response/disease stabilization subjects with vs. without surgery after study drug treatment by using Mann-Whitney tests/ one-way ANOVA (continuous variables) or chisquare/Fisher's Exact tests (categorical variables).

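### Randomisation is stratified by AFP, but the ORR analysis does not use the stratum and no AFP-stratified estimate is planned: a minor loss of precision, not an error

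*Protocol*

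**What the plan says.** **Randomisation.** The Abstract says that the 98 participants "will be 1:1 randomized to study intervention" "and will be stratified by AFP" (below 400 versus 400 or above). AFP is the only stratification factor named. The Abstract also says that first-stage patients are "randomized using block randomization with a block size of 4"; that sentence does not mention AFP.

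**Primary analysis.** Section 11.1 states: "The primary endpoint is ORR in AHCC arm compared to placebo arm". Section 11.3 specifies the decision in full. It is a two-arm BOP2 rule with one Dirichlet prior, and its boundaries are differences in responder and toxicity counts between arms, at 18 and then 47 patients per arm. AFP does not enter it.

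**Other analyses.** Section 11.5 promises 95% confidence intervals for ORR and other rates and names neither a method nor a stratum. Section 11.6 states: "Progression-free survival, time-to-tumor progression, and overall survival will be calculated by the Kaplan-Meier method". It names no between-arm test, hazard ratio or model. In Section 11, AFP appears only in 11.9, as AFP response, which is a grouping formed after baseline and not the randomisation stratum.

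**The concern.** Stratified randomisation removes the part of the between-arm variation that comes from chance imbalance in AFP. An unstratified variance still counts that part. If AFP predicts response, the unstratified interval for the ORR difference is therefore somewhat wider than the design warrants. Choosing AFP as the sole stratifier suggests that the sponsor expects it to matter. With fewer than 50 patients per arm, precision that is already available is worth using. At stake is the width of the interval around the treatment effect. Bias and error control are not at issue.

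**Working it through.** **1. The plan's own figures.** Inputs from the Abstract and Section 11.3: "The null hypothesis assumes a true response rate of 0.27 and a grade 3/4 toxicity rate of 0.57"; "the alternative hypothesis assumes a true response rate of 0.42 and a grade 3/4 toxicity rate of 0.36"; joint probability of response and toxicity 0.15 in both cases; boundaries as printed. Simulating those boundaries (400,000 trials) gives:

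| Quantity | Stated | Reproduced |
|---|---|---|
| Power | 0.75 | 0.752 |
| Type I error | controlled at 0.1 | 0.089 |
| Scenario 1, early stopping | 23.58% | 23.6% |
| Scenario 1, claim promising | 44.40% | 43.6% |
| Scenario 1, average sample size | 80.3 | 80.3 |

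The stated figures come from 10,000 simulations. The standard error of the 44.40% is √(0.444 × 0.556 / 10,000) = 0.5 points, so a 0.8-point difference is compatible with chance.

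**2. The same rule with arms balanced within AFP.** Assume 40% of patients with AFP of 400 or above, and a response odds ratio (low versus high AFP) from 1 to 4. Type I error stays at 0.088 to 0.090, and power runs from 0.753 to 0.764. Ignoring AFP costs the decision rule nothing against its stated performance.

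**3. Precision of the ORR difference.** The Protocol gives neither the AFP split nor the link between AFP and response, so both are assumed. Central case:
- share with AFP of 400 or above: 35%;
- control ORR 10% (high AFP) and 36% (low AFP), overall 0.35 × 0.10 + 0.65 × 0.36 = 0.269, close to the planned 0.27;
- AHCC 15 points higher in each stratum, so 25% and 51%, overall 0.419;
- 49 per arm, balanced within strata.

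Unstratified variance, the sum over arms of p(1 − p):
0.269 × 0.731 + 0.419 × 0.581 = 0.1966 + 0.2434 = 0.440.
Half-width = 1.96 × √(0.440/49) = 18.6 points.

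Stratified variance, the share-weighted sum of p(1 − p) within strata:
- control: 0.35 × 0.10 × 0.90 + 0.65 × 0.36 × 0.64 = 0.1813;
- AHCC: 0.35 × 0.25 × 0.75 + 0.65 × 0.51 × 0.49 = 0.2281;
- sum 0.409, half-width = 1.96 × √(0.409/49) = 17.9 points.

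Reduction in variance: 1 − 0.409/0.440 = 7%.

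**4. Range.** The variance removed is 2 × w(1 − w) × d², where w is the high-AFP share and d the gap in ORR between strata. The treatment effect is again 15 points in each stratum.

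| Assumed case | Removed | Unstratified total | Reduction | Half-width (points) |
|---|---|---|---|---|
| AFP not prognostic | 0 | 0.441 | 0% | 18.6 to 18.6 |
| w = 35%, ORR 15% / 33.5% | 0.016 | 0.441 | 3.5% | 18.6 to 18.3 |
| w = 35%, ORR 10% / 36% | 0.031 | 0.440 | 7% | 18.6 to 17.9 |
| w = 40%, ORR 5% / 42% | 0.066 | 0.442 | 15% | 18.6 to 17.2 |

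**5. PFS, if the arms are compared.** Assume 47 per arm, 6 months of follow-up, median 7 months, treatment hazard ratio 0.6 (about 33 to 35 events) and two-sided 0.05. Log-rank power, unstratified versus stratified, is 0.321 versus 0.319 if AFP has no effect, 0.294 versus 0.309 at an AFP hazard ratio of 2, and 0.265 versus 0.303 at 3 (4,000 simulated trials each). OS was not computed.

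**The case against.** The strongest objection is that this is a preference about a supplementary analysis. A stratified log-rank test, a Cox model and the variance method for an interval are commonly left to the SAP, which is not shown. With arms balanced within strata, the Mantel-Haenszel risk difference equals the crude difference, so only the standard error moves, by 0.7 points of half-width in the central case. That case also assumes a strong AFP effect: the response odds ratio is (0.36/0.64)/(0.10/0.90), about 5. All of this stands, and it is why the point is minor. It does not remove the point, because the primary ORR rule is fully specified in the Protocol and omits the only stratification factor.

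A reader might infer three stronger things that the Protocol does not support.

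- **That every planned comparison wrongly ignores AFP.** For PFS and OS no comparison is specified. Section 11.6 describes Kaplan-Meier estimation only, so there is no survival test that could be conservative.
- **That the trial is losing power.** In the central case a single-look one-sided 10% test of ORR goes from about 61% power unstratified to about 64% stratified. The Protocol contains neither test. Its actual rule delivers the stated 0.75.
- **That stratifying the decision itself would be free.** It would not: a stratified BOP2 rule needs new boundaries and new simulations.

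**Conclusion.** The point holds as a minor inefficiency. AFP is used to randomise and then dropped from the ORR analysis, with no AFP-stratified estimate planned. No error rate is inflated, no estimate is biased, and the BOP2 rule meets its stated operating characteristics. The benefit is a modestly narrower interval for the ORR difference. Over the cases above, the variance falls by between nothing and about 15%, with 7% in the central case. These figures rest on an assumed AFP split, assumed stratum response rates, a constant 15-point effect and balance within strata. The Protocol fixes neither the split nor AFP's prognostic strength.

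**What to change.** Leave the BOP2 boundaries and the go/no-go rule unchanged. Add to Section 11, or to the SAP, that beside the BOP2 decision the between-arm ORR difference is reported as an AFP-stratified Mantel-Haenszel risk difference with 95% CI. Add also that any between-arm comparison of PFS or OS uses a log-rank test and Cox model stratified by AFP (below 400 versus 400 or above). If the sponsor prefers not to use AFP, one sentence should say why.

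The cost is wording. The stratum is known for every patient at randomisation, and no extra data, patients or simulations are needed.
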